2. INTRODUCTION

PF-06651600 is an orally bioavailable, small molecule that is currently being investigated in patients with alopecia areata (AA). PF-06651600 inhibits Janus kinase 3 (JAK3) and the tyrosine kinase family members expressed in hepatocellular carcinoma (TEC) (BTK, BMX, ITK, TEC, TXK), by irreversibly blocking the adenosine triphosphate (ATP) binding site with high selectivity over the other three JAK isoforms (JAK1, JAK2, and tyrosine kinase 2 [TYK2]) as well as over the broader kinome. PF-06651600 potently inhibits signaling of the common gamma (γ)-chain receptors for interleukin (IL)-15 and IL-21, which have been implicated in the pathogenic pathways of AA. Additionally, PF-06651600 inhibits the cytotoxic function of cluster of differentiation (CD)8⁺ T cells and natural killer (NK) cells which have also been implicated in the pathogenic process of AA.^{2,3} This inhibition may be mediated through mechanisms dependent on JAK3 and TEC kinase family members.⁴⁻⁶

See Appendix 10 for vaccine sub-study introduction.

2.1. Study Rationale

PF-06651600 is being developed as an oral treatment for patients with AA based on its mechanism of action, and the clinical results obtained in Phase 1 and Phase 2 studies as outlined below. This study is specifically designed to evaluate the long-term safety, tolerability and efficacy of PF-06651600 in adults and adolescents with AA.

See Appendix 10 for vaccine sub-study rationale.

2.2. Background

AA is a chronic relapsing T-cell mediated autoimmune disorder characterized by non-scarring hair loss affecting children and adults across all ages, races, and sexes.^{7,8} AA is associated with other immune diseases including asthma, allergic rhinitis, atopic dermatitis, and autoimmune diseases such as thyroiditis and vitiligo.⁸

CD8⁺ T cells, NK cells, and mast cells are involved in the pathogenesis of AA. The possible inflammatory pathways in AA include cytokines from the type 1 helper T cell (TH1) axis, including interferon (IFN) alpha (α), IFN gamma (γ), and IFN γ -induced protein 10 (IP-10). Mouse models have shown that IL-2 and IL-15 play a role in the initiation of auto-reactive CD8⁺ cells that attack hair follicles. IL-12 and IL-23 may also play a role in the pathogenesis of AA.

Clinical presentation of AA can be limited to small, circular patches of scalp hair loss (patchy hair loss, alopecia focalis), involve complete loss of hair on the scalp (alopecia totalis [AT]), or total loss of hair on the scalp, face, and body (alopecia universalis [AU]). Patchy alopecia is the most common form of AA which may develop into the more extensive and often treatment-resistant forms of AA, especially with earlier age of onset. It is estimated that AA affects as many as 6 to 7 million individuals in the US and 147 million worldwide.

Further, there is evidence that AA can become refractory to JAK inhibition if it has been present for a substantial period of time. Specifically, a recent case series demonstrated that

AA patients whose current episode of AT or AU had lasted more than 10 years were highly non-responsive to off-label tofacitinib treatment in comparison with patients with shorter duration.¹⁵

Depression, anxiety, and panic disorders are often observed in patients with AA and the coping mechanisms of AA patients mirror those of grief and bereavement. A substantial body of evidence demonstrates a widespread impact of AA on the psychological health of both adult and pediatric patients with AA, including impairment in self-esteem, increased incidence of anxiety and depressive disorders and other psychological conditions, level problems with social relations, decreased health-related quality of life (HRQoL) and general quality of life (QoL), as well as the QoL of their families.

AA is a disease with significant pediatric prevalence, in addition to the burden of disease seen in adults, and ample evidence is available on the impact of AA on the mental health of adolescent patients. In a United States (US) study, children with AA had more psychological problems than those without AA. Specifically, those with AA exhibited more anxiety, depression, tendencies to withdraw, aggression, and delinquency. In addition, children with AA were more likely to exhibit somatic problems as well as problems in social relations and in attention span. Girls with AA seem to be affected more in dimensions of total problems, anxiety/depression, and internalizing/externalizing syndromes. Children with AA were also less likely to have experienced positive life events in the year prior to exhibiting AA symptoms.²³

In addition to experiencing a significant mental health burden, children with AA report experiencing other negative impacts to their QoL. Specifically, 75% of children aged 15-19 years reported instances of effects on QoL, 50% reported that the disease limited their participation in activities, 40% reported instances of bullying, and 35% reported that others noticed and commented on their condition. Rates of decrement in QoL, limitations on participation in activities, and bullying were heightened in older children ages 15-19 years compared to younger children.³³

Given the finding that complete scalp hair loss with duration >10 years in adults is less likely to respond to treatment, it is conceivable that pursuing treatment in younger patients with stable, severe AA may prevent future irreversible hair loss. ¹⁵ Additionally, an earlier age of first onset has been reported to correspond to an increased lifetime risk of extensive disease. Differences in treatment responses are not expected for adolescent versus adult AA patients as suggested in 2 reports of tofacitinib (off-label use). ^{15,34}

No drugs have been approved for the treatment of AA in most countries/regions, including the United States and the European Union (EU). Review of the treatment guidelines and recommendations indicate that a number of off-label therapies are frequently used after assessing factors such as the age of the patient, disease extent, and disease duration. There is neither a cure for AA nor is there a therapy convincingly demonstrated to induce and sustain remission long term. 35-39

2.2.1. Drug Development Rationale

The JAK family, including JAK1, JAK2, JAK3 and TYK2, is a group of cytoplasmic tyrosine kinases that mediate signal transduction via interactions with Type 1 and Type 2 cytokine receptors critical for leukocyte activation, proliferation, survival and function. 40,41 Upon binding of the cytokine to its receptor, the associated JAKs are activated, and phosphorylate each other and the receptor. The phosphorylated receptors serve as docking sites for the signal transducer and activator of transcription (STAT) family of transcription factors. The STATs are phosphorylated and subsequently translocate to the nucleus where they bind to specific gene promoters to activate transcription of a range of target genes. 40,41

JAK1 pairs with JAK3 to mediate γ -common cytokine signaling and also with JAK2 or TYK2 to transmit the signals of additional cytokines important in inflammation and immune responses including IL-2, IL-4, IL-5, IL-6, IL-12, IL-13, IL-15, IL-21, IL-23, IL-31, IFN α , and IFN γ .⁴¹

The cytokine signaling pathways of IFNγ and IL-15, among others, can be blocked via JAK inhibition, supporting the rationale of a JAK inhibitor in the treatment of AA.⁴² Treatment with the JAK inhibitors tofacitinib and ruxolitinib are reported to reverse AA in a mouse model.² Clinically, there are case reports and case series reporting that these JAK inhibitors demonstrate efficacy in AA.^{2,15,43-49}

The tyrosine kinase expressed in hepatocellular carcinoma (TEC) kinase family of protein kinases consists of five members (Bruton's tyrosine kinase [BTK], bone marrow tyrosine kinase on chromosome X [BMX], interleukin 2 inducible T cell kinase [ITK], TEC and tyrosine kinase expressed in T cells [TXK]) primarily expressed in hematopoietic cells. ^{50,51} T cells express three TEC kinases, ITK, TEC and TXK that are activated downstream of the T cell receptor (TCR). BTK plays crucial roles in B cell development and function and is activated downstream of the B cell receptor (BCR). Additionally, TEC kinases have overlapping roles in mediating activation signals in NK cells, mast cells and other hematopoietic cells. ⁵² Since CD8+ T cells, NK cells and mast cells have all been implicated in the pathophysiology of AA^{2,3,10,53} inhibition of TEC kinases has the potential to contribute to efficacy in this disease by modulating the functional activity of pathogenic effector cells.

Based on the mechanism of action of PF-06651600, this candidate is expected to inhibit the signaling of multiple soluble cytokines and signaling pathways contributing to the AA pathogenesis.

2.2.2. Nonclinical and Phase 1 Efficacy and Safety Data

The no observed adverse effect levels (NOAELs) in the 6-month rat and second 9-month dog studies were 200 and 10 mg/kg/day, respectively. In the second 9-month dog toxicity study, the NOAEL of 10 mg/kg/day was based on adverse over-immunosuppression and axonal dystrophy (not axonal degeneration) in the central nervous system and peripheral nervous system at ≥20 mg/kg/day, accompanied by functional auditory deficits (brainstem auditory evoked potentials [BAEP]) at the highest dose of 40 mg/kg/day (a 29-fold exposure multiple relative to the clinical dose of 50 mg). The area under the concentration time curve (AUC)

exposure margins in this second 9-month dog study at the NOAEL at study end were approximately $1.5 \times$ and $6.5 \times$ relative to the predicted exposures at the 200 mg and 50 mg clinical doses, respectively (refer to Table 1).

The potential for PF-06651600 to be involved in drug-drug interactions (DDI) is being investigated. If results exclude a clinically meaningful DDI (eg, relative to AUC [area under the curve]) between PF-65551600 and a perpetrator or victim drug then that perpetrator or victim drug will no longer be prohibited as a prior or concomitant medication based on DDI; this information will be communicated via an administrative letter. Refer to Exclusion Criterion 25, Section 6.5.2, and Section 10.9.1 for medications prohibited to be used prior to and during the study.

PF-06651600 bioequivalence between tablets and capsules was established in completed Phase 1 Study B7981029.

Data from nonclinical and Phase 1 clinical studies, including pharmacokinetics, bioavailability and food effect, support the planned clinical trials with PF-06651600. For a complete description of these studies please refer to the current version of the Investigator's Brochure (IB).

2.2.3. Clinical Experience

There are complete and ongoing Phase 2 and Phase 3 studies with PF-06651600 in a number of disease indications. 42 participants with rheumatoid arthritis (RA) were exposed to PF-06651600 in the Phase 2a Study B7981006. 150 participants with ulcerative colitis were exposed to PF-06651600 in the Phase 2b Study B7981005. 364 and 238 participants with vitiligo in Phase 2b Study B7981019 were exposed to PF-06651600 in the dose-ranging period and in the extension period, respectively. 48 participants were exposed to PF-06651600 in the Phase 2a AA Study B7931005 in the initial 24-week period, and 715 participants with AA were treated with PF-06651600 in the Phase 2b/3 Study B7981015, with key results presented below. There is an ongoing study in participants with Crohn's disease (Phase 2a Study B7981007).

For description and/or results of these studies, please refer to the current version of the PF-06651600 IB.

2.2.3.1. Phase 2a Study in Alopecia Areata

Study B7931005 was a Phase 2a, double-blind, placebo-controlled, multicenter study to evaluate the efficacy and safety profile of PF-06651600 and PF-06700841 (a TYK2/JAK1 inhibitor) compared with placebo in adult (18-75 years old) participants with AA with scalp hair loss of ≥50% at baseline. The study consisted of an initial 24-week double-blind treatment period, an up to 12-month extension period, and a 6-month cross-over open label extension period. A total of 142 participants were randomized to study treatment: 47 participants received placebo, 48 participants received PF-06651600, and 47 participants received PF-06700841.

During the initial 24-week treatment period, participants randomized to PF-06651600 were treated with 200 mg QD during a 4-week induction phase followed by dosing with 50 mg QD in a maintenance phase. The primary efficacy endpoint in the study was change from baseline in Severity of Alopecia Tool (SALT) score at Week 24. Analysis of the initial 24-week treatment period provided data on both efficacy and safety, and indicated clinical improvement with PF-06651600. PF-06651600 met the primary endpoint of change from baseline (CFB) in SALT score. The Mixed Model for Repeated Measures (MMRM) estimates for PF-06651600 compared to placebo at Week 24 for SALT mean CFB (95% CI) were 33.6 [95% CI= (21.4, 45.7); Hochberg p (1-sided) <0.0001]. PF-06651600 differentiated from placebo (statistically significant), as early as Week 6. The placebo response was almost negligible. PF-06651600 also differentiated from placebo on the proportion of responders in absolute SALT score ≤10, eyelash assessment (ELA) and eyebrow assessment (EBA).

During the initial 24-week treatment period of Study B7931005, there were no deaths and no participant in the PF-06651600 treatment group experienced a serious adverse event (SAE). The proportion of participants who experienced treatment-emergent adverse events (TEAEs) in the placebo treatment group (74.5%) was comparable with the PF-06651600 treatment group (62.5%). The TEAEs reported in more than 5% of participants with AA receiving PF-06651600 were headache, infections of upper respiratory tract, acne, diarrhea, nausea, and skin infections. The majority of events were mild. No serious infections, malignancies, cases of herpes zoster, or cases of herpes simplex were reported in the PF-06651600 group.

Hematological changes were observed in both active groups during the induction and maintenance periods, but were not associated with clinically relevant TEAEs. During the induction period, when participants received PF-06651600 200 mg QD for 4 weeks, decreases in mean platelet and lymphocyte counts (-18% and -24% mean CFB, respectively) were observed in the PF-06651600 group. During the maintenance period, when participants received 50 mg QD for 20 weeks, there was improvement in the platelet and lymphocyte counts in the PF-06651600 group (-10% and -9% mean CFB, respectively, at Week 24). Neutrophil counts were increased at Week 4 (12% CFB) and Week 24 (10% CFB) in the PF-06651600 treatment group. Two participants in the PF-06651600 group discontinued due to TEAEs (blood creatine phosphokinase increase and angioedema).

The final study results, including the results of the two extension periods, are described in the current version of the PF-06651600 IB.

2.2.3.2. Phase 2b/3 Study in Alopecia Areata

B7981015 was a Phase 2b/3, randomized, double blind, placebo controlled, dose ranging study to investigate PF-06651600 in both adolescent (≥12 to <18 years old) and adult (≥18 years old) participants with ≥50% scalp hair loss due to AA. The study had a maximum duration of approximately 57 weeks. This included an up to 5-week Screening period, a 48-week treatment period, and a 4-week follow up period. The treatment period was comprised of a placebo-controlled period that included a 4-week loading phase and a 20-week maintenance phase, followed by a 24-week extension phase.

Eligible participants were randomized to blinded PF-06651600 and matching placebo in a 2:2:2:2:1:1:1 (200 mg/50 mg, 200 mg/30 mg, 50 mg, 30 mg, 10 mg, placebo-200 mg/50 mg, and placebo-50 mg, respectively) manner for a total of 7 treatment sequences. All participants began dosing during the loading phase according to their assigned sequence. Following the 4-week loading phase, participants continued dosing according to their assigned sequence in the 20-week maintenance phase. At the end of the maintenance phase, placebo treated participants were advanced in a prespecified, blinded manner to one of 2 active treatment sequences for the remainder of the treatment period (through Week 48).

PF-06651600 200/50 mg, 200/30 mg, 50 mg and 30 mg were significantly superior to placebo at Week 24 on clinician-assessed and patient-reported endpoints related to scalp hair regrowth (including response based on absolute SALT \leq 20, response based on absolute SALT \leq 10, and PGI-C response). Exposure response modelling based on SALT \leq 20 and SALT \leq 10 response at Week 24 showed a positive relationship between dose and response. PF-06651600 200/50 mg, 200/30 mg, 50 mg and 30 mg were also nominally superior to placebo at Week 24 in producing improvement in eyebrows and eyelashes. Continued improvement in efficacy endpoints was seen between Week 24 and Week 48.

The proportion of participants who experienced all-causality TEAEs was similar across treatment groups up to Week 24 (placebo-controlled period) and up to Week 48 (overall). The most frequently reported TEAEs in any group included nasopharyngitis, headache, and upper respiratory tract infection. Up to week 24, the incidence of nasopharyngitis, folliculitis, urticaria, dizziness, upper respiratory tract infection and urinary tract infection was higher in participants treated with PF-06651600 (particularly 200/50 mg and 200/30 mg) than placebo. Most TEAEs were mild to moderate in severity. Fourteen (14) participants experienced 16 SAEs up to Week 48:

- 200/50 mg (4 participants): appendicitis; empyema and sepsis; invasive lobular breast carcinoma, spontaneous abortion.
- 200/30 mg (2 participants): appendicitis; chemical poisoning and suicidal behavior.
- 50 mg (2 participants): breast cancer; pulmonary embolism.
- 30 mg (1 participant): diverticulitis.
- 10 mg (2 participants): suicidal behavior; eczema.
- Placebo-200/50 mg: no SAEs.
- Placebo-50 mg (3 participants): spontaneous abortion; conversion disorder; heavy menstrual bleeding. These treatment-emergent SAEs were all reported during the Placebo-Controlled Period.

Of the 16 SAEs, 12 were considered by the investigator as unrelated to study intervention. The 4 SAEs that were considered related to study intervention in the opinion of the investigator were sepsis and empyema (both in 1 participant); breast cancer; and eczema. There were no deaths in the study.

Treatment with PF-06651600 was associated with changes in hematological parameters, some of which were dose dependent. In the first weeks of the study, there were slight, transient decreases in hemoglobin and small, variable changes in neutrophil and leukocyte

levels. Small, early decreases in platelets were observed with PF-06651600 treatment; these levels remained stable up to Week 48. Dose-dependent early decreases in absolute lymphocyte levels, CD3 (T lymphocytes) and T lymphocyte subsets (CD4 and CD8) were observed. There was a dose-dependent early decrease in CD16/56 (NK cells), particularly in groups who had received a 200 mg loading dose of PF-06651600 for 4 weeks. Overall, there were no clinically meaningful effects of PF-06651600 on ALT, AST, bilirubin, or alkaline phosphatase. The incidence of elevation in hepatic enzymes was low and not dose dependent. Up to Week 48, there were no potential Hy's law cases.

For a complete description and results of this study, please refer to the current version of the PF-06651600 IB.

2.3. Benefit/Risk Assessment

PF-06651600 is an immunomodulator and, as such, can be associated with the potential risk of infection (including serious infection), opportunistic infections, and viral reactivation. The risk of infection is monitored and evaluated in clinical studies of PF-06651600.

In animals, PF-06651600 administration was associated with effects on fetal development including skeletal and visceral organ malformations, and lower fetal body weights. It is not known whether PF-06651600 is secreted into human milk. Because of the investigational nature of PF-06651600, it should not be administered to pregnant women, breastfeeding women, or fertile women of childbearing potential who are unwilling or unable to use contraception as defined in the study protocol. Men in the study are not required to use birth control because PF-06651600 is not likely to transfer to a partner through semen at pharmacologically relevant levels.

In the Phase 2a proof-of-concept Study B7931005 in adult participants with AA, PF-06651600 met its primary endpoint of improvement in SALT score relative to placebo at Week 24. PF-06651600 appeared generally safe and well tolerated. Reductions in platelet counts and lymphocyte counts were observed during treatment with 200 mg QD, but were not considered clinically meaningful and improved after switching to 50 mg QD during the maintenance phase of the study.

These clinical data, including the pivotal Phase 2b/3 B7981015 study described in Section 2.2.3.1, indicate that PF-06651600 at doses up to 200 mg QD for 4 weeks followed by 50 mg QD, has a favorable benefit: risk profile and provides meaningful clinical benefit in a serious disease with no approved treatment options. This study will extend the analysis of benefit: risk for up to 5 years.

The benefit of evaluating PF-06651600 in adolescents was demonstrated in Study B7981015 and is additionally supported by prevalence of AA in adolescents, the significant psychological burden of the disease in this population, and a case series suggesting that extended duration of AA appears to increase likelihood of being refractory to off-label tofacitinib treatment.

See Appendix 10 for vaccine sub-study benefit/risk assessment.

More detailed information about the known and expected benefits and risks and reasonably expected adverse events of PF-06651600 may be found in the current version of the PF-06651600 IB, which is the single reference safety document (SRSD) for this study.

3. OBJECTIVES, ESTIMANDS AND ENDPOINTS

Objectives	Endpoints
Primary	
To evaluate the long-term safety and tolerability of PF-06651600 in adult and adolescent participants with AA.	Through the time the last participant completes the Follow-up visit or 28 days after the Month 36 visit: • Incidence of treatment-emergent adverse events (TEAEs); • Incidence of serious adverse events (SAEs) and adverse events (AEs) leading to discontinuation; • Incidence of clinically significant abnormalities in vital signs; • Incidence of clinically significant abnormalities in clinical laboratory values.
Secondary	
To evaluate the long-term safety and tolerability of PF-06651600 in adult and adolescent participants with AA.	 Through the time of the last participant visit: Incidence of TEAEs; Incidence of SAEs and AEs leading to discontinuation; Incidence of clinically significant abnormalities in vital signs; Incidence of clinically significant abnormalities in clinical laboratory values.

Objectives	Endpoints
To evaluate the long-term efficacy of PF-06651600 in adult and adolescent participants with AA.	 Response based on achieving absolute Severity of Alopecia Tool (SALT) score ≤10 through Month 36, for overall and AA SALT score; Response based on achieving absolute SALT score ≤20 through Month 36, for overall and AA SALT score; Change from baseline in SALT score through Month 36, for overall and AA SALT score; Response based on achieving at least 75% improvement in SALT (SALT75) from baseline through Month 36, for overall and AA SALT score; Response based on achieving at least a 2-grade improvement from baseline or a score of 3 in Eyebrow Assessment (EBA) score through Month 36; Response based on achieving at least a 2-grade improvement from baseline or a score of 3 in Eyelash Assessment (ELA) score through Month 36.
To evaluate the effect of PF-06651600 on patient-centered outcomes and payer relevant measures to assess treatment benefit from the patient perspective and to demonstrate value.	 PGI-C response defined as PGI-C score of "moderately improved" or "greatly improved" through Month 36; Change from baseline in Alopecia Areata Patient Priority Outcomes (AAPPO) scales through Month 36; Change from baseline in the depression subscale score of the Hospital Anxiety and Depression Scale (HADS) through Month 36;

Objectives	Endpoints
	 Change from baseline in the anxiety subscale score of the HADS through Month 36; Improvement on HADS among participants with a baseline subscale score indicative of depression who achieved a "normal" subscale score indicative of an absence of depression through Month 36^{79,90}; Improvement on HADS among participants with a baseline subscale score indicative of anxiety who achieved a "normal" subscale score indicative of an absence of anxiety through Month 36^{79,90}.
Tertiary/Exploratory	
To evaluate the long-term efficacy of PF-06651600 in adult and adolescent participants with AA.	 Response based on achieving at least 50% improvement in SALT (SALT50) from baseline through Month 36, for overall and AA SALT score; Absolute SALT scores through Month 36, for overall and AA SALT score.
	For all scheduled timepoints after Month 36 through Month 60: • Response based on achieving absolute SALT score ≤10, for overall and AA SALT score; • Response based on achieving absolute SALT score ≤20, for overall and AA SALT score; • Change from baseline in SALT score, for overall and AA SALT score; • Response based on achieving at least a 2-grade improvement from

Objectives	Endpoints
	 baseline or a score of 3 in EBA score; Response based on achieving at least a 2-grade improvement from baseline or a score of 3 in ELA score.
To evaluate the effect of PF-06651600 on patient-centered outcomes and payer relevant measures to assess treatment benefit from the patient perspective and to demonstrate value.	 Change from baseline in EuroQoL 5 dimensions (EQ-5D-5L) or EuroQoL 5 dimensions-Youth (EQ-5D-Y) through Month 24; Improvement on PGI-C defined as "slightly improved", "moderately improved", or "greatly improved" through Month 36; Improvement on Patient's Satisfaction with Hair Growth (P-Sat) items defined as slightly, moderately, or very satisfied through Month 36; Change from baseline in Alopecia Areata Resource Utilization (AARU)through Month 24; Change from baseline in Work Productivity and Activity Impairment items: Alopecia Areata (WPAI: AA) through Month 24. Change from baseline in 36-Item Short Form Health Survey version 2 Acute (SF36v2 Acute) through Month 24; Behavior Rating Inventory of Executive Function (BRIEF®2) index scores through Month 36. PGI-C response defined as PGI-C score of "moderately improved" or "greatly improved" after Month 36 through Month 60; Improvement on P-Sat items defined as slightly, moderately, or very

Objectives	Endpoints
	satisfied after Month 36 through Month 60; • BRIEF®2 index scores after Month 36 through Month 60.
To evaluate the long-term efficacy of PF-06651600 in AA nail disease over time.	Change from baseline in fingernails affected by AA through Month 36.
To evaluate the long-term effect of PF-06651600 on the clinician global impression of severity of scalp hair loss.	Change from baseline in the Clinician Global Impression - Alopecia Areata (CGI-AA) through Month 36.
To evaluate pharmacodynamic and disease-related biomarkers over time.	 Change from baseline in lymphocyte subsets (T-cell, B-cell, and natural killer [NK] cells) through Month 36; Change from baseline in immunoglobulins (IgA, IgG, IgM) through Month 36. Change from baseline in lymphocyte subsets (T-cell, B-cell, and NK cells) after Month 36 through Month 60; Change from baseline in immunoglobulins (IgA, IgG, IgM) after Month 36 through Month 60.
PK Objectives	
To characterize the pharmacokinetics of PF-06651600.	Plasma concentrations of PF-06651600 at Month 1 and Month 3.

See Section 9.4.1 and Section 9.4.2 for baseline definition for analyses of efficacy and safety, respectively.

See Appendix 10 for vaccine sub-study objectives and endpoints.

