5.1. Inclusion Criteria

Participants are eligible to be included in the study only if all of the following applicable criteria apply:

5.1.1. Inclusion Criteria for De Novo Participants and Those Originating from B7931005 or B7981015 with >30 Days between the Index Study and Study B7981032

The following inclusion criteria must be met for de novo participants and those originating from B7931005 and B7981015 with >30 days from the first study visit of Study B7981032 and the last dose in the index study.

Type of Participant and Disease Characteristics

- 1. Participants must meet the following AA criteria:
 - Have a clinical diagnosis of AA with no other etiology of hair loss (including, but not limited to traction and scarring alopecia, telogen effluvium). Androgenetic alopecia coexistent with AA is allowed provided that the following criteria are met;
 - For de novo participants ≥12 to <18 years of age at the time of signing of the informed consent/assent: ≥50% terminal scalp hair loss due to AA (including AT and AU), as measured by SALT, at both the screening and Day 1 visits which, in the opinion of the investigator, is appropriate for systemic therapy;

- For de novo participants ≥18 years of age at the time of signing of the informed consent/assent and participants originating from B7931005 or B7981015 with >30 days between the index study and Study B7981032: ≥25% terminal scalp hair loss due to AA (including AT and AU), as measured by SALT, at both the screening and Day 1 visits which, in the opinion of the investigator, is appropriate for systemic therapy;
- Hair loss must be carefully reviewed to verify the required percentage of terminal scalp hair loss is due to AA (ie, SALT [AA] score is ≥25% or ≥50%, as applicable).
 - If, in cases of concomitant AA and androgenetic alopecia, it cannot be verified that the participant has the required SALT (AA) score, then the participant must be excluded from the study.
- No evidence of terminal scalp hair regrowth in areas affected by AA within 6 months of both the screening and Day 1 visits (for de novo participants only);
- Current episode of terminal scalp hair loss due to $AA \le 10$ years (for de novo participants only).

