8.1.2.2. Eyelash Assessment (ELA)

The eyelash assessment (ELA) is a numeric rating scale (NRS) developed to characterize eyelash hair loss. The numeric rating scale ranges from 0 (none) to 3 (normal) as described below.

Score	Description	
0	None Eyelash	
	No eyelashes of both right and left upper and lower eyelashes.	
1	Minimal Eyelash	
	 Modestly or severely decreased density of and/or large gap(s) in one or both upper eyelashes. 	
2	Moderate Eyelash	
	 Normal density of both upper eyelashes without gap(s), and decreased density or gap(s) is present in one or both lower eyelashes, OR 	
	Normal density of both upper eyelashes with short gap(s), OR	
	Mildly decreased density of one or both upper eyelashes with or without short gap(s).	

Score	Description
3	Normal Eyelash
	 Normal density of both right and left upper and lower eyelashes from near medial canthus to near lateral canthus without any gap(s).

NOTE:

- Density of lower eyelashes is usually less than upper eyelashes.
- A short gap does not significantly distort the appearance of the eyelash (es).
- Moderate Eyelash score does not require presence of lower eyelashes.

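### The eyebrow and eyelash response endpoints have no baseline restriction, so a participant already normal at baseline counts as a responder while the score stays normal

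*Protocol*

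**What the plan says.** Protocol Section 3 lists two of the six secondary clinical efficacy endpoints through Month 36 as "Response based on achieving at least a 2-grade improvement from baseline or a score of 3 in Eyebrow Assessment (EBA) score" and "Response based on achieving at least a 2-grade improvement from baseline or a score of 3 in Eyelash Assessment (ELA) score". The exploratory endpoints after Month 36 through Month 60 repeat the rule; the eyebrow bullet again ends "baseline or a score of 3 in EBA score".

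On the eyelash scale, "The numeric rating scale ranges from 0 (none) to 3 (normal) as described below"; the eyebrow scale in Section 8.1.2.3 has the same range and anchors.

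Section 9.3 defines the full analysis set as all participants. Section 9.4.2 makes the efficacy analyses descriptive with 95% two-sided confidence intervals. It sets the efficacy baseline at index-study Day 1 for rollover participants and at Day 1 of this study for de novo participants. It adds no baseline condition for either endpoint.

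The hair-loss entry criterion in Section 5.1.1 is a threshold of 25% or 50% for "terminal scalp hair loss due to AA (including AT and AU), as measured by SALT, at both the screening and Day 1 visits". Section 2.2.3.2 describes the Phase 2b/3 index study as enrolling "participants with ≥50% scalp hair loss due to AA", and Section 2.2.3.1 gives a 50% scalp threshold for the Phase 2a study.

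The same endpoint table does restrict other endpoints by baseline: "Improvement on HADS among participants with a baseline subscale score indicative of depression" is the start of one of the two HADS endpoints on reaching a normal score.

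**The concern.** A participant who starts at 3 cannot improve but meets the second arm of the rule whenever the score is still 3. Such participants can be enrolled, because no eyebrow or eyelash loss is required for entry and Section 2.2 itself says "Clinical presentation of AA can be limited to small, circular patches of scalp hair loss".

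Two comparisons within the endpoint table point to a gap. The HADS endpoints on reaching normal are limited to participants abnormal at baseline. The overall SALT ≤10 and ≤20 endpoints need no such limit, because the scalp thresholds for entry put every participant above the cut-off at the efficacy baseline. The eyebrow and eyelash endpoints have neither protection.

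At stake is what the percentage means. With no control arm, the proportion and its interval are the result, and a reader cannot tell how much of it is regrowth.

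**Working it through.** The protocol gives no expected rate, power or precision for these endpoints, so there is no figure to reproduce.

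**Step 1. Apply the rule to every baseline score.** Response means (visit score − baseline ≥ 2) or (visit score = 3).

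| Baseline score | Visit scores that count as response |
|---|---|
| 0 | 2, 3 |
| 1 | 3 |
| 2 | 3 |
| 3 | 3 |

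The score-of-3 arm is needed: from baseline 1 or 2 the only responding score is 3, and from baseline 2 a two-grade gain is impossible. The problem is the last row only. Rollover participants who reached 3 during the index study are genuine improvers, because their baseline is index-study Day 1.

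**Step 2. Size.** Let q be the share at 3 at baseline, s the share of those still at 3 at the visit, and r the response rate among those starting below 3.

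Written rate = q·s + (1 − q)·r, so written rate − r = q(s − r).

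The documents give none of q, s or r; every value below is an assumption.

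| q | s | r | Difference (percentage points) |
|---|---|---|---|
| 10% | 90% | 40% | 0.10 × 0.50 = +5.0 |
| 10% | 90% | 60% | 0.10 × 0.30 = +3.0 |
| 10% | 90% | 75% | 0.10 × 0.15 = +1.5 |
| 10% | 90% | 90% | 0 |
| 10% | 70% | 75% | 0.10 × (−0.05) = −0.5 |
| 20% | 50% | 75% | 0.20 × (−0.25) = −5.0 |

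Over q = 5–30%, s = 50–100% and r = 20–90%, the minimum is 0.30 × (0.50 − 0.90) = −12 points and the maximum is 0.30 × (1.00 − 0.20) = +24 points. The sign is positive when s exceeds r and negative when it does not.

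**Step 3. Compare with sampling error.** Find the q at which q(s − r) equals the half-width 1.96·√[p(1 − p)/n], with p = q·s + (1 − q)·r and s = 90%. The totals 960 and 450 (de novo) are in Section 9.2; 200 is an assumed size for Treatment Period 2.

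| r | n = 960 | n = 450 | n = 200 |
|---|---|---|---|
| 40% | 6.3% | 9.2% | 13.8% |
| 60% | 10.2% | 14.7% | 21.8% |
| 75% | 17.6% | 25.2% | 36.6% |

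As a check on the first cell: p = 0.063 × 0.9 + 0.937 × 0.4 = 0.4315, the half-width is 1.96·√(0.4315 × 0.5685/960) = 3.1 points, and the difference is 0.063 × 0.5 = 3.15 points.

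The figure 960 is an upper limit. Attrition, the separate cohort displays, the exclusion of observation-period data from the summaries (Section 9.4.2) and restricted entry to Treatment Period 2 (Section 4.1) all lower n.

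**The case against.** The strongest reply is that the protocol delegates this detail. Sections 9.4 and 9.4.2 leave analysis populations and further details to the statistical analysis plan. The SAP on hand covers only the vaccine sub-study, so the main-study SAP may already restrict the denominator. That stands as a limit: the finding concerns the protocol text, not how the data were or will be analysed. It does not remove the point, because Section 3 states a complete rule and following it gives the mixture.

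A second reply is that nothing shows participants at baseline 3 are common. Scalp loss of at least 25% or 50% is required, totalis and universalis are included, and the index-study eligibility lists are not available, only summaries. This also stands. That such participants can enter follows for de novo participants from the criteria here and for rollovers from those summaries; their number is unknown.

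Third, the proportion with normal or much improved eyebrows is a legitimate status measure in a relapsing disease, and efficacy is descriptive and not primary. True, but the endpoint is worded as response, and the percentage does not show its two components.

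Fourth, redefining secondary endpoints in an open-label study with data accruing has a credibility cost, and a display by baseline score would answer the concern. The cost is limited, because a restriction on a score recorded at baseline is not driven by outcome. Reporting both groups also lets the rate under the current wording be reconstructed.

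**Conclusion.** The point holds for the protocol as written. Two of six secondary clinical efficacy endpoints, and their exploratory counterparts at Months 48 and 60, count unchanged normal scores as response. Neither size nor direction can be determined from the documents; the −12 to +24 point range rests entirely on assumed q, s and r. No hypothesis test, power or error rate is involved, so the consequence is for interpreting the percentages and their intervals. It should be fixed, with medium confidence because the main-study SAP was not available.

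**What to change.** First check the main-study SAP. If it already restricts the denominator, align the protocol wording with it. If not, define eyebrow response among participants with baseline EBA below 3 and eyelash response among those with baseline ELA below 3, keeping the Section 9.4.2 baseline (index-study Day 1 for rollovers). Apply this both through Month 36 and after Month 36 through Month 60. Report the proportion maintaining a score of 3 separately for participants who started at 3.

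The change is one phrase per endpoint and uses scores already collected. The price is a smaller denominator, n(1 − q). Half-widths at a 50% rate, in percentage points, from 1.96·√[0.25/(n(1 − q))]:

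| n | q = 0 | q = 10% | q = 30% |
|---|---|---|---|
| 960 | 3.2 | 3.3 | 3.8 |
| 450 | 4.6 | 4.9 | 5.5 |
| 200 (assumed) | 6.9 | 7.3 | 8.3 |

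The change should be dated and made before database lock, with its basis in baseline scores stated.
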